16.3 Required Imaging Studies

16.3.1 CT or MRI of the abdomen and pelvis

CT and MRI guidelines are available on the COG Member site at: https://members.childrensoncologygroup.org/_files/reference/RefMaterial/DiagnosticImagingGuidelines_MRI&CT.pdf

CT of the abdomen and pelvis should be collimated to at most 5 mm slice thickness. IV contrast in the portal venous phase (usually around 50s post-injection) is required. Oral contrast is not necessary.

MRI of the abdomen and pelvis should include T1 and T2 weighted images pre-contrast and post-contrast dynamic T1-weighted images through the kidneys. Diffusion weighted images are strongly recommended. Recommended b values for diffusion weighted imaging are b 50, 500, 1000 mm/s². Post contrast T1 weighted images through the kidneys should be acquired dynamically in the arterial (~20s), portal venous (~50s) and delayed phase. **Note:** The same imaging parameters should be used at each evaluation.

16.3.2 CT of the chest

CT of the chest should have enhanced lung windows. IV contrast is encouraged at diagnosis to assess for possible mediastinal adenopathy. Slice thickness should be 5 mm or less.

17.0 RADIATION THERAPY GUIDELINES

No radiation therapy is planned for this study.

APPENDIX I: CTEP AND CTSU REGISTRATION PROCEDURES**INVESTIGATOR AND RESEARCH ASSOCIATE REGISTRATION WITH CTEP**

Food and Drug Administration (FDA) regulations and National Cancer Institute (NCI) policy require all individuals contributing to NCI-sponsored trials to register and to renew their registration annually. To register, all individuals must obtain a Cancer Therapy Evaluation Program (CTEP) Identity and Access Management (IAM) account at <https://ctepcore.nci.nih.gov/iam>. In addition, persons with a registration type of Investigator (IVR), Non-Physician Investigator (NPIVR), or Associate Plus (AP) must complete their annual registration using CTEP's web-based Registration and Credential Repository (RCR) at <https://ctepcore.nci.nih.gov/rer>.

RCR utilizes five person registration types.

- IVR — MD, DO, or international equivalent;
- NPIVR — advanced practice providers (e.g., NP or PA) or graduate level researchers (e.g., PhD);
- AP — clinical site staff (e.g., RN or CRA) with data entry access to CTSU applications such as the Roster Update Management System (RUMS), OPEN, Rave, acting as a primary site contact, or with consenting privileges;
- Associate (A) — other clinical site staff involved in the conduct of NCI-sponsored trials; and
- Associate Basic (AB) — individuals (e.g., pharmaceutical company employees) with limited access to NCI-supported systems.

RCR requires the following registration documents:

Documentation Required	IVR	NPIVR	AP	A	AB
FDA Form 1572	✓	✓			
Financial Disclosure Form	✓	✓	✓		
NCI Biosketch (education, training, employment, license, and certification)	✓	✓	✓		
GCP training	✓	✓	✓		
Agent Shipment Form (if applicable)	✓				
CV (optional)	✓	✓	✓		

An active CTEP-IAM user account and appropriate RCR registration is required to access all CTEP and Cancer Trials Support Unit (CTSU) websites and applications. In addition, IVRs and NPIVRs must list all clinical practice sites and Institutional Review Boards (IRBs) covering their practice sites on the FDA Form 1572 in RCR to allow the following:

- Addition to a site roster;
- Assign the treating, credit, consenting, or drug shipment (IVR only) tasks in OPEN;
- Act as the site-protocol Principal Investigator (PI) on the IRB approval; and
- Assign the Clinical Investigator (CI) role on the Delegation of Tasks Log (DTL).

In addition, all investigators acting as the Site-Protocol PI (investigator listed on the IRB approval), consenting/treating/drug shipment investigator in OPEN, or as the CI on the DTL must be rostered at the enrolling site with a participating organization.

Additional information is located on the CTEP website at <https://ctep.cancer.gov/investigatorResources/default.htm>. For questions, please contact the RCR *Help Desk* by email at [contact].

CTSU REGISTRATION PROCEDURES

This study is supported by the NCI Cancer Trials Support Unit (CTSU).

Downloading Site Registration Documents:

Download the site registration forms from the protocol-specific page located on the CTSU members' website. Permission to view and download this protocol and its supporting documents is restricted based on person and site roster assignment. To participate, the institution and its associated investigators and staff must be associated with the LPO or a Protocol Organization (PO) on the protocol. One way to search for a protocol is listed below.

- Log in to the CTSU members' website (<https://www.ctsu.org>) using your CTEP-IAM username and password;
- Click on *Protocols* in the upper left of the screen
 - Enter the protocol number in the search field at the top of the protocol tree; or
 - Click on the By Lead Organization folder to expand, then select *COG*, and protocol number (*insert study number*).
- Click on *Documents*, select *Site Registration*, and download and complete the forms provided.
(Note: For sites under the CIRB, IRB data will load automatically to the CTSU.)

Protocol-Specific Requirements For Site Registration:

- IRB approval (For sites not participating via the NCI CIRB; local IRB documentation, an IRB-signed CTSU IRB Certification Form, Protocol of Human Subjects Assurance Identification/IRB Certification/Declaration of Exemption Form, or combination is accepted)

Submitting Regulatory Documents:

Submit required forms and documents to the CTSU Regulatory Office using the Regulatory Submission Portal on the CTSU website.

To access the Regulatory Submission Portal log in to the CTSU members' website, go to the Regulatory section and select Regulatory Submission.

Institutions with patients waiting that are unable to use the Regulatory Submission Portal should alert the CTSU Regulatory Office immediately at [name] in order to receive further instruction and support.

Checking Your Site's Registration Status

Site registration status may be verified on the CTSU members' website.

- Click on *Regulatory* at the top of the screen;
- Click on *Site Registration*; and
- Enter the site's 5-character CTEP Institution Code and click on Go.
 - Additional filters are available to sort by Protocol, Registration Status, Protocol Status, and/or IRB Type.

Note: The status shown only reflects institutional compliance with site registration requirements as outlined within the protocol. It does not reflect compliance with protocol requirements for individuals participating on the protocol or the enrolling investigator's status with NCI or their affiliated networks.

Data Submission / Data Reporting

Medidata Rave is a clinical data management system being used for data collection for this trial/study. Access to the trial in Rave is controlled through the CTEP-IAM system and role assignments.

Requirements to access Rave via iMedidata:

- A valid CTEP-IAM account; and
- Assigned a Rave role on the LPO or PO roster at the enrolling site of: Rave CRA, Rave Read Only, Rave CRA (LabAdmin), Rave SLA, or Rave Investigator.

Rave role requirements:

- Rave CRA or Rave CRA (Lab Admin) role must have a minimum of an Associate Plus (AP) registration type;
- Rave Investigator role must be registered as an Non-Physician Investigator (NPIVR) or Investigator (IVR); and
- Rave Read Only role must have at a minimum an Associates (A) registration type.

Refer to <https://ctep.cancer.gov/investigatorResources/default.htm> for registration types and documentation required.

Rave-CTEP-AERS Integration

The Rave Cancer Therapy Evaluation Program Adverse Event Reporting System (CTEP-AERS) Integration enables evaluation of post-baseline Adverse Events (AE) entered in Rave to determine whether they require expedited reporting, and facilitates entry in CTEP-AERS for those AEs requiring expedited reporting.

All AEs that occur after baseline are collected in Medidata Rave using the Adverse Event form, which is available for entry at each treatment or reporting period and used to collect AEs that start during the period or persist from the previous reporting period. CRA will enter AEs that occur prior to the start of treatment on a baseline form that is not included in the Rave-CTEP-AERS integration. AEs that occur prior to enrollment must begin and end on the baseline Adverse Events form and should not be included on the standard Adverse Events form that is available at treatment unless there has been an increase in grade.

Prior to sending AEs through the rules evaluation process, site staff should verify the following on the Adverse Event form in Rave:

- The reporting period (course/cycle) is correct; and
- AEs are recorded and complete (no missing fields) and the form is query free.

The CRA reports AEs in Rave at the time the Investigator learns of the event. If the CRA modifies an AE, it must be re-submitted for rules evaluation.

Upon completion of AE entry in Medidata Rave, the CRA submits the AE for rules evaluation by completing the Expedited Reporting Evaluation form. Both NCI and protocol-specific reporting rules

evaluate the AEs submitted for expedited reporting. A report is initiated in CTEP-AERS using information entered in Medidata Rave for AEs that meet reporting requirements. The CRA completes the report by accessing CTEP-AERS via a direct link on the Medidata Rave Expedited Reporting Evaluation form.

In the rare occurrence that Internet connectivity is lost, a 24-hour notification is to be made to CTEP by telephone at [contact]. Once internet connectivity is restored, the 24-hour notification that was phoned in must be entered immediately into CTEP-AERS using the direct link from Medidata Rave.

Additional information about the CTEP-AERS integration is available on the CTSU website:

- Study specific documents: Protocols > Documents > Education and Promotion; and
- Expedited Safety Reporting Rules Evaluation user guide: Resources > CTSU Operations Information > User Guides & Help Topics.

NCI requirements for SAE reporting are available on the CTEP website:

- NCI Guidelines for Investigators: Adverse Event Reporting Requirements is available at https://ctep.cancer.gov/protocolDevelopment/electronic_applications/docs/aeguidelines.pdf

Data Quality Portal

The Data Quality Portal (DQP) provides a central location for site staff to manage unanswered queries and form delinquencies, monitor data quality and timeliness, generate reports, and review metrics.

The DQP is located on the CTSU members' website under Data Management. The Rave Home section displays a table providing summary counts of Total Delinquencies and Total Queries. DQP Queries, DQP Delinquent Forms and the DQP Reports modules are available to access details and reports of unanswered queries, delinquent forms, and timeliness reports. Review the DQP modules on a regular basis to manage specified queries and delinquent forms.

The DQP is accessible by site staff that are rostered to a site and have access to the CTSU website. Staff that have Rave study access can access the Rave study data using a direct link on the DQP.

To learn more about DQP use and access, click on the Help icon displayed on the Rave Home, DQP Queries, and DQP Delinquent Forms modules.

Note: Some Rave protocols may not have delinquent form details or reports specified on the DQP. A protocol must have the Calendar functionality implemented in Rave by the Lead Protocol Organization for delinquent form details and reports to be available on the DQP. Site staff should contact the LPO Data Manager for their protocol regarding questions about Rave Calendaring functionality.

APPENDIX II: PERFORMANCE STATUS SCALES/SCORES

Performance Status Criteria					
Karnofsky and Lansky performance scores are intended to be multiples of 10					
ECOG (Zubrod)		Karnofsky		Lansky*	
Score	Description	Score	Description	Score	Description
0	Fully active, able to carry on all pre-disease performance without restriction.	100	Normal, no complaints, no evidence of disease	100	Fully active, normal.
		90	Able to carry on normal activity, minor signs or symptoms of disease.	90	Minor restrictions in physically strenuous activity.
1	Restricted in physically strenuous activity but ambulatory and able to carry out work of a light or sedentary nature, e.g., light housework, office work.	80	Normal activity with effort; some signs or symptoms of disease.	80	Active, but tires more quickly
		70	Cares for self, unable to carry on normal activity or do active work.	70	Both greater restriction of and less time spent in play activity.
2	Ambulatory and capable of all self-care but unable to carry out any work activities. Up and about more than 50% of waking hours	60	Required occasional assistance, but is able to care for most of his/her needs.	60	Up and around, but minimal active play; keeps busy with quieter activities.
		50	Requires considerable assistance and frequent medical care.	50	Gets dressed, but lies around much of the day; no active play, able to participate in all quiet play and activities.
3	Capable of only limited self-care, confined to bed or chair more than 50% of waking hours.	40	Disabled, requires special care and assistance.	40	Mostly in bed; participates in quiet activities.
		30	Severely disabled, hospitalization indicated. Death not imminent.	30	In bed; needs assistance even for quiet play.
4	Completely disabled. Cannot carry on any self-care. Totally confined to bed or chair.	20	Very sick, hospitalization indicated. Death not imminent.	20	Often sleeping; play entirely limited to very passive activities.
		10	Moribund, fatal processes progressing rapidly.	10	No play; does not get out of bed.

*The conversion of the Lansky to ECOG scales is intended for NCI reporting purposes only.

APPENDIX III: BLOOD PRESSURE FOR PATIENTS < 18 YEARS OLD BY AGE AND HEIGHT

Blood pressure (BP) levels for BOYS

Age	BP	Systolic Blood Pressure, mm Hg							Diastolic Blood Pressure, mm Hg						
		Percentile of Height							Percentile of Height						
(years)	Percentile	5th	10th	25th	50th	75th	90th	95th	5th	10th	25th	50th	75th	90th	95th
1	95th	98	99	101	103	104	106	106	54	54	55	56	57	58	58
2	95th	101	102	104	106	108	109	110	59	59	60	61	62	63	63
3	95th	104	105	107	109	110	112	113	63	63	64	65	66	67	67
4	95th	106	107	109	111	112	114	115	66	67	68	69	70	71	71
5	95th	108	109	110	112	114	115	116	69	70	71	72	73	74	74
6	95th	109	110	112	114	115	117	117	72	72	73	74	75	76	76
7	95th	110	111	113	115	117	118	119	74	74	75	76	77	78	78
8	95th	111	112	114	116	118	119	120	75	76	77	78	79	79	80
9	95th	113	114	116	118	119	121	121	76	77	78	79	80	81	81
10	95th	115	116	117	119	121	122	123	77	78	79	80	81	81	82
11	95th	117	118	119	121	123	124	125	78	78	79	80	81	82	82
12	95th	119	120	122	123	125	127	127	78	79	80	81	82	82	83
13	95th	121	122	124	126	128	129	130	79	79	80	81	82	83	83
14	95th	124	125	127	128	130	132	132	80	80	81	82	83	84	84
15	95th	126	127	129	131	133	134	135	81	81	82	83	84	85	85
16	95th	129	130	132	134	135	137	137	82	83	83	84	85	86	87
≥17	95th	131	132	134	136	138	139	140	84	85	86	87	87	88	89

Instructions for using this BP Chart:

1. Measure the patient's blood pressure using an appropriate size cuff.
2. Select appropriate chart for a female or male patient.
3. Using the "age" row and "height" column to determine if the BP is within the ULN.
4. See [Section 5.1.2.9](#) for definition of dose limiting hypertension, [Section 5.2.5](#) for management and grading of hypertension, and [Section 4.2.8](#) for medical treatment of axitinib related hypertension.

This table was taken from "The Fourth Report on the Diagnosis, Evaluation, and Treatment of High Blood Pressure in Children and Adolescents" [PEDIATRICS](#) Vol. 114 No. 2 August 2004, pp. 555-576.

Blood pressure (BP) levels for GIRLS

Age	BP	Systolic Blood Pressure, mm Hg							Diastolic Blood Pressure, mm Hg						
		Percentile of Height							Percentile of Height						
(years)	Percentile	5th	10th	25th	50th	75th	90th	95th	5th	10th	25th	50th	75th	90th	95th
1	95th	100	101	102	104	105	106	107	56	57	57	58	59	59	60
2	95th	102	103	104	105	107	108	109	61	62	62	63	64	65	65
3	95th	104	104	105	107	108	109	110	65	66	66	67	68	68	69
4	95th	105	106	107	108	110	111	112	68	68	69	70	71	71	72
5	95th	107	107	108	110	111	112	113	70	71	71	72	73	73	74
6	95th	108	109	110	111	113	114	115	72	72	73	74	74	75	76
7	95th	110	111	112	113	115	116	116	73	74	74	75	76	76	77
8	95th	112	112	114	115	116	118	118	75	75	75	76	77	78	78
9	95th	114	114	115	117	118	119	120	76	76	76	77	78	79	79
10	95th	116	116	117	119	120	121	122	77	77	77	78	79	80	80
11	95th	118	118	119	121	122	123	124	78	78	78	79	80	81	81
12	95th	119	120	121	123	124	125	126	79	79	79	80	81	82	82
13	95th	121	122	123	124	126	127	128	80	80	80	81	82	83	83
14	95th	123	123	125	126	127	129	129	81	81	81	82	83	84	84
15	95th	124	125	126	127	129	130	131	82	82	82	83	84	85	85
16	95th	125	126	127	128	130	131	132	82	82	83	84	85	85	86
≥17	95th	125	126	127	129	130	131	132	82	83	83	84	85	85	86

Instructions for using this BP Chart:

1. Measure the patient's blood pressure using an appropriate size cuff.
2. Select appropriate chart for a female or male patient.
3. Using the "age" row and "height" column to determine if the BP is within the ULN.
4. See [Section 5.1.2.9](#) for definition of dose limiting hypertension, [Section 5.2.5](#) for management and grading of hypertension, and [Section 4.2.8](#) for medical treatment of axitinib related hypertension.

This table was taken from "The Fourth Report on the Diagnosis, Evaluation, and Treatment of High Blood Pressure in Children and Adolescents" [PEDIATRICS](#) Vol. 114 No. 2 August 2004, pp. 555-576.

APPENDIX IV: AXITINIB DOSING NOMOGRAMS FOR PATIENTS < 18 YEARS OLD**Axitinib Dose Level -1: 1.8 mg/m²/dose PO BID**

BSA (m ²)	Total Daily Dose	AM Dose	PM Dose
0.53-0.69	2 mg	1 mg	1 mg
0.70-0.97	3 mg	2 mg	1 mg
0.98-1.35	4 mg	2 mg	2 mg
1.36-1.56	5 mg	3 mg	2 mg
1.57-1.97	6 mg	3 mg	3 mg
≥ 1.98	7 mg	4 mg	3 mg

Axitinib Dose Level 1 (STARTING DOSE): 2.4 mg/m²/dose PO BID

BSA (m ²)	Total Daily Dose	AM Dose	PM Dose
0.53-0.69	3 mg	2 mg	1 mg
0.70-0.93	4 mg	2 mg	2 mg
0.94-1.14	5 mg	3 mg	2 mg
1.15-1.35	6 mg	3 mg	3 mg
1.36-1.56	7 mg	4 mg	3 mg
1.57-1.77	8 mg	4 mg	4 mg
1.78-1.97	9 mg	5 mg	4 mg
≥ 1.98	10 mg	5 mg	5 mg

Axitinib Dose Level 2 (Dose Titration)

[figure not shown]
BSA (m ²)	Total Daily Dose	AM Dose	PM Dose
0.53-0.69	4 mg	2 mg	2 mg
0.70-0.93	5 mg	3 mg	2 mg
0.94-1.14	6 mg	3 mg	3 mg
1.15-1.35	8 mg	4 mg	4 mg
1.36-1.56	9 mg	5 mg	4 mg
1.57-1.77	10 mg	5 mg	5 mg
1.78-1.97	11 mg	6 mg	5 mg
≥ 1.98	12 mg	6 mg	6 mg

Axitinib Dose Level 3 (Dose Titration)

BSA (m ²)	Total Daily Dose	AM Dose	PM Dose
0.53-0.69	5 mg	3 mg	2 mg
0.70-0.93	6 mg	3 mg	3 mg
0.94-1.14	8 mg	4 mg	4 mg
1.15-1.35	10 mg	5 mg	5 mg
1.36-1.56	11 mg	6 mg	5 mg
1.57-1.77	12 mg	6 mg	6 mg
1.78-1.97	13 mg	7 mg	6 mg
≥ 1.98	14 mg	7 mg	7 mg

APPENDIX V: BRISTOL MYERS SQUIBB NIVOLUMAB TREATMENT GUIDELINES ALGORITHM**Endocrinopathy Management Algorithm**

[figure not shown]
Rule out non-inflammatory causes. If non-inflammatory cause, treat accordingly and continue immuno-oncology (I-O) therapy.
Consider visual field testing, endocrinology consultation, and imaging.

Patients on IV steroids may be switched to an equivalent dose of oral corticosteroids (e.g. prednisone) at start of tapering or earlier, once sustained clinical improvement is observed. Lower bioavailability of oral corticosteroids should be taken into account when switching to the equivalent dose of oral corticosteroids.

GI Adverse Event Management Algorithm

[figure not shown]
Rule out non-inflammatory causes. If non-inflammatory cause is identified, treat accordingly and continue I-O therapy. Opiates/narcotics may mask symptoms of perforation. Infliximab should not be used in cases of perforation or sepsis.

Patients on IV steroids may be switched to an equivalent dose of oral corticosteroids (e.g. prednisone) at start of tapering or earlier, once sustained clinical improvement is observed. Lower bioavailability of oral corticosteroids should be taken into account when switching to the equivalent dose of oral corticosteroids.

Hepatic Adverse Event Management Algorithm

Rule out non-inflammatory causes. If non-inflammatory cause, treat accordingly and continue I-O therapy. Consider imaging for obstruction.

Patients on IV steroids may be switched to an equivalent dose of oral corticosteroids (e.g. prednisone) at start of tapering or earlier, once sustained clinical improvement is observed. Lower bioavailability of oral corticosteroids should be taken into account when switching to the equivalent dose of oral corticosteroids.

[figure not shown]
*I-O therapy may be delayed rather than discontinued if AST/ALT ≤ 8 x ULN and T.bili ≤ 5 x ULN.

**The recommended starting dose for grade 4 hepatitis is 2 mg/kg/day methylprednisolone IV.

Note: The dosing of any medications above are provided for patients ≥ 18 years of age.

Neurological Adverse Event Management Algorithm

[figure not shown]
Rule out non-inflammatory causes. If non-inflammatory cause, treat accordingly and continue I-O therapy.

Patients on IV steroids may be switched to an equivalent dose of oral corticosteroids (e.g. prednisone) at start of tapering or earlier, once sustained clinical improvement is observed. Lower bioavailability of oral corticosteroids should be taken into account when switching to the equivalent dose of oral corticosteroids.

Pulmonary Adverse Event Management Algorithm

[figure not shown]
Rule out non-inflammatory causes. If non-inflammatory cause, treat accordingly and continue I-O therapy. Evaluate with imaging and pulmonary consultation.

Patients on IV steroids may be switched to an equivalent dose of oral corticosteroids (e.g. prednisone) at start of tapering or earlier, once sustained clinical improvement is observed. Lower bioavailability of oral corticosteroids should be taken into account when switching to the equivalent dose of oral corticosteroids.

Renal Adverse Event Management Algorithm

[figure not shown]
Rule out non-inflammatory causes. If non-inflammatory cause, treat accordingly and continue I-O therapy

Patients on IV steroids may be switched to an equivalent dose of oral corticosteroids (e.g. prednisone) at start of tapering or earlier, once sustained clinical improvement is observed. Lower bioavailability of oral corticosteroids should be taken into account when switching to the equivalent dose of oral corticosteroids.

Skin Adverse Event Management Algorithm

Rule out non-inflammatory causes. If non-inflammatory cause, treat accordingly and continue I-O therapy.

Patients on IV steroids may be switched to an equivalent dose of oral corticosteroids (e.g. prednisone) at start of tapering or earlier, once sustained clinical improvement is observed. Lower bioavailability of oral corticosteroids should be taken into account when switching to the equivalent dose of oral corticosteroids.
*Refer to NCI CTCAE v4 for term-specific grading criteria.

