5.2.1.2 For patients $<$ 18 years of age

See [Appendix IV](#) for dosing nomograms and titrations.

Dose Level	Axitinib Dose (mg/m ² /dose PO BID)
-1 [#]	1.8 (max 4 mg/dose BID)
1*	2.4 (max 5 mg/dose BID)
2	See dose titration in Appendix IV
3	See dose titration in Appendix IV

* Starting dose

[#] If a patient was most recently dosed at the lowest dose level and requires a subsequent dose reduction, the patient must be removed from protocol therapy.

5.2.2 It is recognized that to avoid high grade toxicities, periodic breaks from axitinib dosing may benefit patients. In general, such breaks of up to 7 days per cycle will be permitted at the discretion of the treating physician. Such breaks may be considered for non-DLT related recurrent toxicities impacting a patient's quality of life.

5.2.3 If a patient experiences a Grade 4 neutropenia or Grade 4 thrombocytopenia, axitinib will be withheld. Counts should be checked twice weekly until \leq Grade 3.

5.2.3.1 If the toxicity resolves to meet eligibility or baseline within 7 days of drug discontinuation, axitinib may be restarted either at the same dose level or at one dose level lower (see [Section 5.2.1](#)) at the discretion of the treating physician. For delays of more than 7 and up to 21 days, dose reduction is required. Doses reduced for toxicity will not be re-escalated, even if there is minimal or no toxicity at the lower dose level.

5.2.3.2 If toxicity does not resolve to meet eligibility or baseline within 21 days of drug discontinuation, the patient must be removed from protocol therapy.

5.2.4 If a patient experiences Grade 3 or 4 non-hematologic toxicity, axitinib should be held until toxicity resolves to \leq Grade 2. If the toxicity resolves to \leq Grade 2 within 7 days, axitinib may be restarted either at the same dose level or at one dose level lower (see [Section 5.2.1](#)) at the discretion of the treating physician. For delays of more than 7 and up to 21 days, dose reduction is required. For delays of more than 21 days, the patient must be removed from protocol therapy.

5.2.5 **Dose Modifications for Hypertension:**

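### The paediatric axitinib Dose Level -1 table falls 1 mg/day below its own 1.8 mg/m² heading in four BSA ranges, and its top row never gives the maximum stated in Section 5.2.1.2

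*Combined protocol and SAP*

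**What the plan says.** Section 5.2.1.2 lists the paediatric dose levels per m². Level -1 is "1.8 (max 4 mg/dose BID") and the starting level is "2.4 (max 5 mg/dose BID"). The section refers the reader to Appendix IV for the nomograms. Level -1 is the lowest paediatric level, and a patient who needs a further reduction leaves protocol therapy.

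Appendix IV heads its reduced-dose table "Axitinib Dose Level -1: 1.8 mg/m²/dose PO BID". The rows used below are these:

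- Level -1 includes "0.70-0.97 3 mg 2 mg 1 mg" and "0.98-1.35 4 mg 2 mg 2 mg", then 5 mg at 1.36-1.56 and 6 mg at 1.57-1.97. Its last row is "≥ 1.98 7 mg 4 mg 3 mg".
- The starting-dose table includes "0.94-1.14 5 mg 3 mg 2 mg" and ends with "≥ 1.98 10 mg 5 mg 5 mg".

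Section 6.1 says that axitinib comes as 1 mg and 5 mg tablets, and Section 4.3.3 says that they may not be cut. Every dose is therefore a whole number of mg. Neither Appendix IV nor Section 5.2.1.2 states how the mg/m² figure is rounded.

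**The concern.** The starting-dose table behaves as a rounded mg/m² table should: its limits follow from 2.4 mg/m² and its top row equals its stated maximum. The Level -1 table begins that way and then changes. Its first two limits follow from 1.8 mg/m², and the remaining three coincide with limits of the 2.4 mg/m² table. A table that departs from its own heading leaves a site unable to tell whether the heading or the rows express the intended dose.

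The maximum raises the same question for the largest patients. Section 5.2.1.2 names a ceiling that the table never reaches. The dose-reduction rules in Section 5.2 point to Section 5.2.1, which carries both the mg/m² figure and the reference to Appendix IV. The therapy delivery map in Section 4.3.1 asks for a calculated dose to be entered. No text says which source prevails if they differ. At stake is whether dose-reduced children of the same size receive the same dose at different sites.

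**Working it through.** **Inputs.** Level -1: 1.8 mg/m²/dose twice daily, or 2 × 1.8 = 3.6 mg/m²/day, with a maximum of 2 × 4 = 8 mg/day (Section 5.2.1.2). Level 1: 2 × 2.4 = 4.8 mg/m²/day, with a maximum of 2 × 5 = 10 mg/day. Printed totals come from Appendix IV. The assumed rule is to round the daily total to the nearest whole mg, halves up, at each 0.01 m².

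**Does the rule fit the table that is not in dispute?** For Level 1, 4.8 × BSA rounded to the nearest mg equals the printed total at 142 of the 145 BSA values from 0.53 to 1.97 m². The exceptions are 0.70-0.72 m². The top row equals the 10 mg/day maximum. The rule is therefore a fair reading of how that table was built.

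**Where should the Level -1 limits fall?** A total changes from k to k+1 mg at BSA = (k + 0.5)/3.6:

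- 2.5/3.6 = 0.694 and 3.5/3.6 = 0.972. Printed limits: 0.69/0.70 and 0.97/0.98. These agree.
- 4.5/3.6 = 1.25, 5.5/3.6 = 1.528 and 6.5/3.6 = 1.806. Printed limits: 1.35/1.36, 1.56/1.57 and 1.97/1.98. These do not agree.
- The same three printed limits do follow from 2.4 mg/m²: 6.5/4.8 = 1.354, 7.5/4.8 = 1.5625 and 9.5/4.8 = 1.979.
- 7.5/3.6 = 2.083 would start an 8 mg row. None is printed.

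**Size of the departure.**

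| BSA (m²) | 3.6 × BSA (mg/day) | Nearest mg | Printed | Printed v unrounded, upper end |
|---|---|---|---|---|
| 1.25-1.35 | 4.50-4.86 | 5 | 4 | 1 - 4/4.86 = 18% low |
| 1.53-1.56 | 5.51-5.62 | 6 | 5 | 1 - 5/5.62 = 11% low |
| 1.81-1.97 | 6.52-7.09 | 7 | 6 | 1 - 6/7.09 = 15% low |
| from 2.09 | 7.52, capped at 8 | 8 | 7 | 1 - 7/8 = 12.5% low |

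From 0.53 to 1.97 m², the printed Level -1 total equals the rounded figure at 113 of 145 values. It is 1 mg lower at the other 32 (11 + 4 + 17) and never higher. At 1.95-1.97 m² it is lower than rounding down would give: 3.6 × 1.95 = 7.02, printed 6.

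**The maximum.** Unrounded, 1.8 mg/m² reaches 4 mg/dose at 4/1.8 = 2.22 m². With the daily total rounded, 8 mg/day is reached from 2.09 m². The table gives 7 mg/day at every BSA from 1.98 m².

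**The step from Level 1 to Level -1.** The nominal step is 1 - 1.8/2.4 = 25%. The printed tables give 20% at 0.98-1.14 m² (5 to 4 mg) and 40% at 0.94-0.97 m² (5 to 3 mg), with all other bands in between. In both of those ranges the Level -1 total equals 1.8 mg/m² correctly rounded: 3.53-4.10 gives 4, and 3.38-3.49 gives 3. Setting 1.8 mg/m² rounded throughout against the printed Level 1 table gives steps of 14% to 40%, which is wider.

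**The case against.** The strongest reply is that nearest-mg rounding at every 0.01 m² is the reader's assumption. Rounding 3.6 × BSA at each band's midpoint (2.20, 3.01, 4.19, 5.26, 6.37) reproduces all five closed rows, and 3.6 × 1.98 = 7.13 gives the 7 mg of the top row. Section 5.2.1.2 sends the reader to Appendix IV, as do Sections 4.1 and 4.3.3, so a site would normally read the table. A maximum is also only an upper limit: 4 mg in the morning reaches it, 3 mg in the evening lies below it, and nothing exceeds it.

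Much of this stands. No stated maximum is breached, and most BSA values match the heading. But the midpoint account takes the bands as given, and the bands are what is in question. A whole-mg step at 1.8 mg/m² needs bands about 1/3.6 = 0.28 m² wide, whereas the four closed bands from 0.70 m² span 0.28, 0.38, 0.21 and 0.41. The top row also needs a different rule (lower limit instead of midpoint).

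Three stronger readings are tempting, and the documents do not support them:

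- That the table error produces the 20% to 40% spread in step size. Both extremes fall where the table follows 1.8 mg/m². They come mainly from whole 1 mg tablets.
- That the paediatric pharmacokinetic work (Aim 1.3.4) is compromised because dose level mislabels exposure. Section 9.3 plans a population analysis of measured concentrations, nothing makes dose level the exposure measure, and the therapy delivery map records BSA and the mg given.
- That retention on axitinib is altered. Level -1 is the last level before removal, but the documents give nothing from which to estimate such an effect.

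**Conclusion.** The point holds as an internal inconsistency in a dosing table. On nearest-mg rounding of the daily total, Level -1 is 1 mg/day below its heading in three closed BSA ranges and from about 2.09 m². The shortfall against the unrounded figure reaches 18% at 1.35 m² and 15% at 1.97 m². It is always in the same direction, and the affected bands carry the limits of a different dose level.

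The disagreement with Section 5.2.1.2 over the maximum is narrower. It concerns dose-reduced patients under 18 with a BSA of about 2.09 m² or more, for whom the two places imply 8 and 7 mg/day. The exact ranges depend on the assumed rounding rule, which fits the starting-dose table almost everywhere but is not written down. The result at 1.95-1.97 m² does not depend on choosing nearest-mg over rounding down. This is worth correcting because sites dose from the table. It does not touch the primary analysis.

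**What to change.** The sponsor must reconcile three things: the Level -1 rows in Appendix IV, the 1.8 mg/m² heading above them, and the 4 mg BID maximum in Section 5.2.1.2. The amended text should state the rounding rule behind the nomograms and say whether Appendix IV or Section 5.2.1.2 governs where they differ. Whether the rows, the heading or the maximum changes is a clinical decision for the sponsor, and no view is taken here on which dose is right. The cost is one table or its heading and one line in Section 5.2.1.2, by amendment, with no added procedures or data collection.
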